8.1. Number of Participants

An estimated number of 20-25 patients affected by TAAD and undergoing open heart surgery are usually admitted in mid/high-volume aortic centres (1). Therefore, it is estimated that the registry will encompass more than 5000 patients in total. Locally, the number of patients admitted to Glenfield Hospital (University Hospitals of Leicester NHS Trust) fulfilling the inclusion criteria between 1 January 2010 and 31 December 2025 is (average) 15-20 per year.

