8.3. Statistical Analysis

Statistical analyses will be conducted using Stata v. 15.1 (StataCorp LLC, Texas, USA) and SPSS v. 29.0 (IBM Corporation, Armonk, NY, USA) statistical softwares. Continuous variables and outcomes will be summarized as mean and standard deviation as well as median and interquartile range. Categorical variables and outcomes will be reported as counts and percentages. A p<0.05 will be set for statistical significance. Differences between the study groups will be evaluated using the Fisher's exact test, the Chi-square test, the linear-by-linear association test, the Mann-Whitney test and the Kruskal-Wallis test. The McNemar test and paired samples T-test will be used in case of

analysis of paired groups. Propensity score matching will be performed to balance treatment strategies for baseline differences. A propensity score will be estimated using a non-parsimonious multilevel mixed-effects logistic regression considering the cluster effect of the participating centers whose results may be affected by the referral pathway, surgical techniques and perioperative care. Multilevel mixed-effects logistic regression model will include all available baseline variables. One-to-one propensity score matching will be performed using a caliper width of 0.2 of the standard deviation of the estimated logit. Standardized differences <0.10 will be considered an acceptable imbalance between the matched cohorts. The estimated propensity score will be also included into regression models to adjust for multiple confounders or for analysis within its strata.

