Logistic and linear regression analyses will be employed to identify independent risk factors for early adverse events with and without a stepwise approach. For the purpose of developing a risk scoring method from this registry, the study cohort will be randomly divided into two datasets, i.e. the derivation data set (75.0% of patients) and the validation data set (25.0% of patients). Univariate analysis will be performed on all candidate covariates of the derivation dataset to identify predictors of in-hospital mortality. Multiple logistic regression analysis will be then performed using the derivation dataset. A stepwise procedure with a bootstrap approach will be used, and 100 samples will be extracted with a size of 70% of the derivation dataset. A stepwise procedure will be applied to each sample (probability to stay = 0.05; probability to entry = 0.1). Variables selected in at least 50% of the stepwise procedures will be included in the regression model. Additional covariates were selected using a forward selection comparing the Akaike information criterion for the models with and without each covariate. The model with the lowest Akaike information criterion will be selected for each forward step, until the inclusion of a new covariate determined an increase in the Akaike information criterion value. The model will be tested in the validation data set for calibration, using the Hosmer-Lemeshow test, and for discrimination using the receiver-operating characteristic curve analysis. A comparison of the predictive ability of the new score with the current risk scoring methods for prediction of in-hospital mortality will be performed in the overall dataset as well as in the validation dataset using the DeLong test. The improvement of discrimination of the new score will be estimated by calculating the net reclassification index and the integrated discrimination improvement.

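### NRI and IDI are assigned to estimate the gain in discrimination, but both also respond to calibration differences, in either direction, and no recalibration of the existing scores is stated

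*Protocol*

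**What the plan says.** Section 8.3 (Statistical Analysis) develops an in-hospital mortality score on a random 75% of the registry and keeps 25% for validation. Three statements matter here.

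- Comparison with existing scores: "A comparison of the predictive ability of the new score with the current risk scoring methods for prediction of in-hospital mortality will be performed". The method and the data are given as: "will be performed in the overall dataset as well as in the validation dataset using the DeLong test".
- Size of the gain: "The improvement of discrimination of the new score will be estimated by calculating the net reclassification index and the integrated discrimination improvement".
- Calibration, stated for the new model only: "The model will be tested in the validation data set for calibration, using the Hosmer-Lemeshow test".

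The general threshold in the same section is "A p<0.05 will be set for statistical significance". The protocol does not name the comparator scores, say how their predicted risks are obtained, mention recalibrating them, or say which form of NRI is meant.

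**The concern.** Discrimination is how well a score ranks patients who die above patients who survive. NRI and IDI do not isolate it. They compare the risks that two scores assign, so they move when one score is systematically too high, too low, too flat or too extreme, even if the ranking is equally good.

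A calibration difference is to be expected. The new score takes its intercept and coefficients from this registry, and the existing scores were built elsewhere. A random split of the same cohort does not remove this, so the problem is present in the untouched 25% and is separate from any re-use of derivation data.

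At stake is a comparative claim about mortality scores. The same paragraph can yield a DeLong test with no difference and a large NRI or IDI labelled as a change in discrimination, and the text does not say which governs the claim.

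**Working it through.** The protocol gives no NRI or IDI figure to reproduce. The check asks what these measures do when discrimination is equal.

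**Inputs from the protocol.** Section 8.1 says "it is estimated that the registry will encompass more than 5000 patients in total", so the validation set is 0.25 x 5000 = 1250. The synopsis and section 13.3 give more than 10000, so 0.25 x 10000 = 2500. Mortality is set near 17%, the 30-day figure of a database cited in section 5.1, as a proxy for in-hospital mortality. Alpha is 0.05, taken as two-sided.

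**Assumptions not in the protocol.** The form and size of the comparators' miscalibration, AUCs of about 0.73 to 0.76, and category cut-offs at 10/20/30%.

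**Formulas.**
- IDI = (mean new risk in deaths − mean new risk in survivors) − (the same difference for the old score).
- NRI = [P(up | death) − P(down | death)] + [P(down | survivor) − P(up | survivor)]. Up means a higher risk (continuous form) or a higher category (categorical form) under the new score.
- AUC depends on ranks only.

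**By hand.** Take two patients with new-score risks of 30% and 10%, a gap of 20.0 points.
- Old score with odds halved: 0.4286/2 = 0.2143, risk 17.6%; 0.1111/2 = 0.0556, risk 5.3%. The gap is 12.4 points, so the new score looks better by 7.6.
- Old score with odds doubled: 0.8571, risk 46.2%; 0.2222, risk 18.2%. The gap is 28.0 points, so the new score looks worse by 8.0.
- The ranking is the same throughout. With odds halved, every patient moves up under the new score, so continuous NRI = (+1) + (−1) = 0.

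**Simulation 1: old score is a monotone transform of the new one, so AUC is identical** (400 runs, n = 2500, AUC about 0.76). Percentages are runs significant for or against the new score.

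| Old score | IDI | Continuous NRI | Categorical NRI |
|---|---|---|---|
| Odds halved | +0.045 (for, 100%) | 0.00 (0%) | +0.17 (for, 100%) |
| Too flat, spread x0.5 | +0.079 (for, 100%) | +0.74 (for, 100%) | +0.35 (for, 100%) |
| Odds doubled | −0.041 (against, 100%) | 0.00 (0%) | +0.10 (for, 75%) |
| Too extreme, spread x1.5 | −0.072 (against, 100%) | −0.74 (against, 100%) | −0.08 (against, 92%) |

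The AUC difference is 0 in every row. With odds doubled, IDI and categorical NRI point in opposite directions.

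**Simulation 2: two different scores with equal true AUC, about 0.745** (400 runs). With both calibrated, IDI and both NRI forms average about zero, and each favours the new score in 2.5 to 4% of runs. With the old score too flat (x0.5, n = 2500), IDI is +0.067 and continuous NRI +0.40, both significant in 100%. A pure shift leaves continuous NRI near zero. DeLong rejects in about 4 to 7% (two-sided), whatever the calibration.

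**Simulation 3: new score fitted on the 75%, two scores with equal AUC of about 0.73 and correlation 0.7.** It was run independently more than once; ranges span the runs. Results favouring the new score have a nominal rate of 2.5%.
- Old score too low by 0.7 on the logit, spread x0.7, n = 2500: IDI 100%, continuous NRI 96 to 98%, categorical NRI 100%, DeLong about 3%.
- Same, n = 1250: 100%, 80 to 86%, and just under 100%.
- Milder (−0.4, spread x0.85), n = 2500: 100%, 63 to 68%, 83 to 86%, DeLong 3 to 4%.
- Old score too high by 0.7: IDI against the new score in 98 to 99%.
- Old score too extreme (x1.4): IDI and continuous NRI against it in 99 to 100%.
- Too low and too flat, after recalibrating intercept and slope in the derivation set: 3 to 8% per measure.

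Continuous NRI also depends on how closely the two scores agree. For a score with odds halved and spread x0.7 at n = 2500, it was +0.04 and never significant in simulation 1, but +0.15 and significant in 90% of runs in simulation 2.

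**The case against.** **DeLong is already planned.** It is unaffected by monotone miscalibration. NRI and IDI are only to be estimated, with no test attached and no decision rule resting on them; reading them as significant relies on the section's general threshold. This stands and limits the consequence. It does not remove the defect, because the sentence on the size of the gain in discrimination names NRI and IDI, not the AUC difference.

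**Details may be in an analysis plan.** The NRI form, the comparators and any recalibration are commonly left there, and a comparator with classes only would need a local mapping to risk, which is itself a recalibration. It is therefore an inference that published risks will be used unchanged. What the protocol does fix is the label: these measures are to estimate discrimination.

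**A stronger reading is tempting.** A reader might infer that NRI and IDI simply reward better calibration, so that the locally fitted score will be declared more discriminating. The documents do not support this. The sign depends on the direction of miscalibration, and a better-calibrated new score can be penalised. Section 5.1 reports that early mortality has declined, which, if anything, suggests that older scores overstate risk, the direction in which IDI went against the new score. Nor does every calibration error move both measures: a pure shift leaves continuous NRI near zero.

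**The score is not a listed objective or outcome.** True. It is one analysis among the 42 studies expected in section 14.

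**Conclusion.** The concern holds in a conditional form. As written, section 8.3 assigns the gain in discrimination to two measures that can show a significant gain or a significant loss between scores of equal AUC. Under the assumed distortions the effect is large: for several of them at n = 2500, IDI and at least one form of NRI are significant in nearly every run, while DeLong stays near its nominal level.

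The percentages rest on assumed miscalibration. The protocol gives no calibration data for any existing score, so direction and size in this registry are unknown. It does not follow that the new score will be favoured. What follows is that NRI and IDI cannot be read as discrimination here, and that no rule covers disagreement with DeLong. The point is secondary to the registry's main objectives but worth correcting before the scores are compared.

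**What to change.** In section 8.3 (Statistical Analysis):

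1. Define the gain in discrimination as the difference in c-statistic between the new and each existing score, with its 95% CI (DeLong), in the validation dataset.
2. If NRI and IDI are kept, first recalibrate each existing score (intercept and slope) in the derivation dataset and compute both measures in the validation dataset. Report them descriptively, separately for deaths and survivors, and do not label them discrimination.
3. Report the calibration of the existing scores as a result in its own right.

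The cost is about two sentences and one two-parameter logistic refit per existing score, with no new data. The downside is that the apparent gain of the new score may change, in either direction.

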Statistical	Continuous variables will be reported as mean and standard deviation or		
Considerations	median and interquartile range as needed. Dichotomous and nominal variables		
	will be reported as counts and percentages. Univariate analysis will be		
	performed using the Mann-Whitney U test, Student's t-test, Kruskall-Wallis test,		
	Wilcoxon test, Fisher exact test, Chi-square test, Kaplan-Meier test.		
	Multivariable analyses will be performed using logistic, classification tree,		
	linear and ordinal regression methods. A Bayesian hierarchical approach will		
	be used in case of significant between center variability.		

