Interinstitutional and between-surgeons differences in terms of early outcomes will be evaluated using logistic regression. The risk-adjusted rate of adverse binary events at each center will be estimated by dividing the observed number of adverse events by the expected number of adverse events, and by multiplying this ratio by the average event rate of the overall series. The expected numbers of adverse events will be calculated with logistic regression. The estimated risk-adjusted rates of adverse events will be summarized as odds ratios and their 95% confidence intervals in caterpillar plots with the x-axis ordered for increasing adjusted rates.

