13.2 Limitations

The retrospective nature is the main limitation of this registry. However, our aim is to investigate the long-term outcome (>10 years) of these patients and this may not be feasible with a prospective registry. Second, the prognostic impact of different treatment strategies will be analyzed using several statistical methods to adjust for baseline differences. However, the lack of randomization does not prevent the effects of confounding variables. Third, perioperative care may significantly vary between institutions as well as individual surgeons and their effects should be considered in all analyses.

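### Section 8.3 computes a standardised rate for each centre but reports it as an odds ratio, and the outcome models allow for centre only if between-centre variability is significant

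*Protocol*

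**What the plan says.** Section 8.3 (Statistical Analysis) opens the centre comparison with "Interinstitutional and between-surgeons differences in terms of early outcomes will be evaluated using logistic regression". Each centre's result is observed over expected events, turned into a rate "by multiplying this ratio by the average event rate of the overall series". On the source of the denominator it says "The expected numbers of adverse events will be calculated with logistic regression". The results are then to be presented as follows: "The estimated risk-adjusted rates of adverse events will be summarized as odds ratios and their 95% confidence intervals in caterpillar plots". The centres in the plot are to be sorted by the adjusted rate, not by the odds ratio shown. No conversion from rate to odds ratio is given, and no reference for the odds ratio.

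On clustering, the protocol says different things in different places:

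- Section 8.3 specifies a multilevel model with centre as the cluster for the propensity score, because centres differ in referral, technique and care.
- The risk-factor models for early events in the same section are called only logistic and linear regression.
- The Synopsis alone adds a Bayesian hierarchical model, and makes it conditional: it is to "be used in case of significant between center variability". It names no test or threshold, and section 8.3 does not repeat the condition.
- Section 13.2 says that "perioperative care may significantly vary between institutions as well as individual surgeons and their effects should be considered in all analyses".

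**The concern.** The first problem is one of measure. A standardised rate is a percentage, whereas an odds ratio compares odds with a reference. A reader of the plot who takes the plotted value as the observed/expected ratio, or as a relative rate, would think a centre more extreme than it is. An interval built for one measure does not serve the other.

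The second problem is how dependence within centres is handled. Section 8.3 says multilevel where it means it, so the bare term logistic regression is fairly read as single-level, though that remains an inference. A single-level model treats patients of one centre as independent. For a factor that varies mainly between centres, its standard error is then too small. This bears on the search for predictors of early mortality and complications, not only on the centre plots. A hierarchical model that depends on a significant test also cannot meet a statement that centre and surgeon effects belong in every analysis.

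**Working it through.** **1. Rate against odds ratio.** The protocol gives no numerical centre result, so there is no figure of its own to reproduce. Input: overall event rate p = 0.17, the 30-day mortality that section 5.1 cites from the largest of its three series (the other two give 16.9% and 18%). The overall average is taken as the reference, an assumption because the protocol names none.

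Rate r = (O/E) × p. Odds ratio = [r/(1 − r)] / [p/(1 − p)], with 0.17/0.83 = 0.2048.

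| O/E | Rate r | r/(1 − r) | Odds ratio |
|---|---|---|---|
| 0.5 | 8.5% | 0.0929 | 0.45 |
| 1.5 | 25.5% | 0.3423 | 1.67 |
| 2.0 | 34.0% | 0.5152 | 2.52 |

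The odds ratio is always further from 1 than O/E, and the gap grows with the event rate. For O/E = 1.5 it is 1.59 at p = 10% and 1.91 at p = 30%. Converting each rate against one common p would keep the order of centres. Odds ratios taken from a regression need not follow the order of the adjusted rates.

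**2. Are the centre-specific intervals too narrow?** A simulation used 2000 runs per scenario, p = 17%, equal centre sizes and no case-mix. Sizes were 32 centres × 312 (10000/32, from the Synopsis), 20 × 250 (5000/20, from sections 7.1 and 8.1) and 20 × 200. The between-centre SD of the log-odds is not in the documents and was varied from 0 to 0.5. Single-level 95% intervals for a centre's own log-odds covered 94.7% to 95.3% throughout. At 32 × 312 and SD 0.3 their mean width was 0.60, against 0.53 for shrunken intervals. So they are not too narrow.

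**3. A factor constant within each centre, with no true effect.** For scale, at p = 17% one SD either side of the average is about 15.6% to 18.5% for SD 0.1, and 14.4% to 20.0% for SD 0.2.

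An approximate check at 312 per centre uses ICC ≈ SD² × 0.17 × 0.83 = SD² × 0.1411, design effect = 1 + 311 × ICC, and type I error ≈ 2[1 − Φ(1.96/√design effect)]. The test is taken as two-sided at 5%.

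| SD | ICC | Design effect | Square root | Type I, approx. | Type I, simulated (32 × 312) |
|---|---|---|---|---|---|
| 0.1 | 0.0014 | 1.44 | 1.20 | 10.2% | 9.5% |
| 0.2 | 0.0056 | 2.76 | 1.66 | 23.8% | 23.4% |

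With 20 × 250 the simulated values are 8.8% and 19.0%. All of these are for a model that ignores centre, so they take no account of the Synopsis condition.

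**4. Would the condition catch it?** The protocol names no test, so a 5% chi-square test of heterogeneity is assumed. At SD 0.1 it is significant in 42.0% of runs (32 × 312) or 23.5% (20 × 250). At SD 0.2 the figures are 98.5% and 84.8%. At SD 0.1 the single-level model would therefore be kept in more than half of the runs, while its type I error is nearly twice the nominal level.

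**The case against.** Five points can be made against the concern.

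- O/E times the overall rate is a legitimate standardised estimate. A reader might infer from the mislabelling that the centre estimates are wrong. The documents do not support that, because the fault lies in what the estimate is called and how it is reported. The passage could even be meant as two outputs: odds ratios from the regression, plotted in order of the adjusted rates. That stands, but the sentence as written says that the rates themselves become odds ratios, so it still needs correcting.
- A reader might infer that the plotted intervals are too narrow because the model is single-level. Step 2 contradicts this for the centre's own result.
- With marked heterogeneity the Synopsis condition would nearly always bring in the hierarchical model. That stands, and it confines the damage to modest heterogeneity. It does so only if the condition is carried out with a reasonable test.
- Random-effects structure and interval methods can be left to an analysis plan. That is fair for the details. It does not excuse a reporting rule that equates two measures, or a conditional rule set beside an unconditional statement.
- Section 13.2 discusses limitations and fixes no model, and centre comparison is not a listed objective. Both are true. The mislabelling therefore leaves the primary results untouched, but the risk-factor models do serve the primary objective for early mortality.

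**Conclusion.** The concern holds in two limited parts. First, the reporting rule in section 8.3 is wrong as written. At 17% mortality the two measures differ by 1.67 against 1.5, 2.52 against 2.0, and 0.45 against 0.5. This is arithmetic and rests only on taking the overall average as reference. Second, clustering is treated inconsistently across section 8.3, the Synopsis and section 13.2. For a purely centre-level factor, ignoring it gives a type I error of about 9.5% to 23% at an assumed SD of 0.1 to 0.2. These figures are illustrative. They assume equal centres and no case-mix, and the error rate of the whole procedure with the condition in force was not calculated.

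A larger figure is tempting. With an assumed ICC of 0.01 to 0.05, √(1 + 311 × ICC) suggests standard errors understated 2.0 to 4.1 fold, and a reader might apply that to cannulation, perfusion or arch strategy. The documents do not support this, for two reasons. The formula holds only for factors constant within a centre, and section 7.7 records these choices patient by patient. If the factor's own ICC is 0.2 (assumption), √(1 + 311 × 0.2 × ICC) gives 1.27 to 2.03. Also, SDs of 0.3 to 0.5 correspond to ICCs of about 0.013 to 0.035, and there the heterogeneity test was significant in 99% to 100% of runs, so the single-level model would usually have been abandoned.

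**What to change.** In section 8.3, choose one measure for the centre plots and use it for the estimate, the interval and the ordering. It can be either of these:

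- the standardised rate, with a confidence interval for that rate; or
- centre odds ratios against the overall average, from a mixed-effects logistic model and labelled as such.

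If expected counts come from a model with a centre effect, compute them with that effect set to zero. Otherwise O/E is pulled towards 1.

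Put a random centre intercept in the outcome and risk-factor models, with surgeon nested in centre where surgeons are compared. Remove the significance condition from the Synopsis so that it agrees with sections 8.3 and 13.2.

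The cost is protocol wording and somewhat more computation, with no new data. Some intervals for centre-driven factors will widen. If shrunken centre odds ratios are chosen, their intervals should allow for uncertainty in the between-centre variance. The simple empirical-Bayes intervals in the simulation covered only 84.3% at SD 0.1 and 93.0% at SD 0.2 (32 × 312).

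### Centre results are defined as indirectly standardised rates (observed/expected times the overall rate) but are to be reported as odds ratios, with no reference group or conversion.

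*Protocol*

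**What the plan says.** Section 8.3 (Statistical Analysis) sets out the centre comparison in four steps.

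- Model: "Interinstitutional and between-surgeons differences in terms of early outcomes will be evaluated using logistic regression".
- Estimator: "The risk-adjusted rate of adverse binary events at each center will be estimated by dividing the observed number of adverse events by the expected number" and then "by multiplying this ratio by the average event rate of the overall series". For the denominator, "The expected numbers of adverse events will be calculated with logistic regression"; no centre effect is mentioned.
- Reporting scale: "The estimated risk-adjusted rates of adverse events will be summarized as odds ratios and their 95% confidence intervals in caterpillar plots".
- Display: the plot is drawn "with the x-axis ordered for increasing adjusted rates".

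The estimator is worded for centres. Surgeons appear only in the opening sentence, under logistic regression.

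Two other places bear on this. The synopsis (Statistical Considerations) says that a Bayesian hierarchical approach will "be used in case of significant between center variability", without naming a test or threshold. Earlier in section 8.3, a multilevel mixed-effects logistic model that allows for clustering by centre is planned, but for the propensity score.

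**The concern.** The protocol fixes both the estimator and the scale on which it is reported, and the two do not match. Observed over expected, times the overall event rate, is a rate. An odds ratio compares the odds in one group with the odds in another, so it needs a named comparator and either a conversion or a model that yields it. Section 8.3 gives none of these for the plotted quantity.

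Two analysts following the text could therefore plot different things under the same axis label: the observed/expected ratio itself, an odds ratio converted from the adjusted rate, or a centre coefficient from a logistic model. The confidence interval would differ too. Readers of the registry's centre comparison would then take a ratio of rates for an odds ratio, or the reverse, and the error grows with the frequency of the outcome. The method is stated for adverse binary events in general, so commoner complications fall within its scope as well as death.

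A second, smaller matter is that the synopsis and section 8.3 are not tied together. It is unclear whether the ordered plot shows raw or hierarchically estimated centre results.

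**Working it through.** The protocol gives no figure for this point, so there is nothing to reproduce.

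**Inputs**

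- Overall event rate m = 0.17: the 30-day mortality of the largest series cited in section 5.1, used for illustration.
- Centres: 32 (synopsis). Section 7.1 says 20.
- Patients per centre: 300. This is 20 a year for 15 years (2010 to 2024), using the upper end of the one local volume given in section 8.1 (15 to 20 a year). Equal centre sizes are an assumption. The synopsis total of 10000 over 32 centres gives a similar 312.
- A mean of 50%: an assumption, standing for a common complication.

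**Step 1: the three measures**

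Adjusted rate r = m × O/E. Odds ratio against the overall series = [r/(1−r)] / [m/(1−m)]. At m = 0.17 the reference odds are 0.17/0.83 = 0.2048.

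| O/E | Adjusted rate | Odds ratio |
|---|---|---|
| 0.5 | 8.5% | 0.45 |
| 0.75 | 12.75% | 0.71 |
| 1.25 | 21.25% | 1.32 |
| 1.5 | 25.5% | 1.67 |
| 2.0 | 34.0% | 2.52 |

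For O/E = 1.5: 0.255/0.745 = 0.3423, and 0.3423/0.2048 = 1.67.

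**Step 2: a commoner outcome**

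At m = 0.50 the reference odds are 1. O/E = 1.3 gives a rate of 65% and an odds ratio of 0.65/0.35 = 1.86. O/E = 1.5 gives 75% and an odds ratio of 0.75/0.25 = 3.00, against 1.67 for the same O/E at 17%.

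**Step 3: even the converted figure is not the model's odds ratio**

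Suppose patients' log-odds of the event are normal with mean −1.9 and SD 1.0 (assumed; mean risk 16.8%), and a centre's true case-mix-adjusted odds ratio is 1.5. Simulation gives O/E = 1.328, hence a rate of 0.17 × 1.328 = 22.6%. Converting that rate gives (0.226/0.774)/0.2048 = 1.43, not 1.5. So the text has to name the source of its odds ratio, not only the label.

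**Step 4: spread of unshrunken centre rates by chance**

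I drew 20,000 sets of binomial counts with a true risk of 17% in every centre and averaged the lowest and highest rates in each set.

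| Centres × patients | Mean lowest | Mean highest |
|---|---|---|
| 32 × 300 | 12.7% | 21.6% |
| 32 × 312 | 12.7% | 21.5% |
| 32 × 225 (15 a year) | 12.0% | 22.3% |
| 20 × 250 | 12.7% | 21.5% |

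With 32 centres of 300, the highest rate is on average about 1.7 times the lowest with no true difference. For one such centre, the 95% limits for O/E under no difference are 1 ± 1.96 × √(300 × 0.17 × 0.83)/(300 × 0.17) = 1 ± 1.96 × 0.1276, that is 0.75 to 1.25.

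**The case against.** The best defence is that this is loose wording and not a wrong analysis. The section opens by saying that differences between institutions will be assessed by logistic regression, which can produce centre odds ratios with intervals. On that reading the plot shows those odds ratios and uses the adjusted rates only to order the axis. The reading is possible, but it is not what the sentence says: it is the adjusted rates that are to be summarised as odds ratios. The objection softens the consequence, since a wrong measure in print is a risk and not a certainty. It does not remove the need to correct the text.

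On the ordering, the defence is stronger. The plot carries 95% intervals, which exist to show the chance variation in step 4. No league table or outlier rule is announced. Indirect standardisation without shrinkage is a legitimate choice, and the synopsis does foresee a hierarchical model. Whether that model feeds this plot could be settled in a statistical analysis plan that is not shown. What stands is that the synopsis and section 8.3 should be reconciled.

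The impact is also limited. Comparing centres is not among the listed objectives or outcomes, and the mislabelling does not touch the predictor, propensity-score or risk-score analyses.

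Three stronger readings are tempting and are not supported:

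- That surgeons too will be given observed/expected rates and ranked. The calculation is worded for each centre, and the protocol gives no surgeon volumes.
- That no odds ratio can be obtained without a different model. Step 1 converts the rate to one algebraically, wherever the rate lies strictly between 0 and 100%. The fault is that no conversion or comparator is stated.
- That leaving out shrinkage is in itself an error. It is a defensible choice if made openly.

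**Conclusion.** The point holds for centres. The rule as written computes an indirectly standardised rate and calls it an odds ratio, without a reference group or conversion. At a 17% mean the difference is moderate near the average (O/E 1.25 against an odds ratio of 1.32) and larger further out (2.0 against 2.52). At an assumed 50% mean it is substantial (1.5 against 3.00).

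The link to the hierarchical approach is secondary. The range of 12.7% to 21.6% rests on equal centres of 300 patients, a common 17% risk and no case-mix variation. It shows why the text should say whether the ordered estimates are shrunken; it does not show that the planned display is invalid.

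This should be corrected, but it does not threaten the registry's main analyses.

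**What to change.** In section 8.3 (Statistical Analysis), choose one measure and describe it completely:

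- **Keep the present estimator.** Plot the observed/expected ratio or the risk-adjusted rate under that name, with an interval derived for that quantity, and drop the term odds ratio; or
- **Report odds ratios.** Fit a logistic model with the case-mix covariates and a random centre intercept, and plot the exponentiated centre effect with its 95% interval as the odds ratio against the average centre.

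In either case, add one sentence saying whether the synopsis's hierarchical approach applies to this plot and, if its use stays conditional, what counts as significant variability between centres.

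The cost is a few lines of text. The second option uses a model type that section 8.3 already plans for the propensity score; its small downside is that low-volume centres are pulled towards the mean. No data collection changes.
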